1.1 Background

i) Introduction and Feasibility

Hypotension that fails to respond to the current armamentarium of vasopressors is a common complication after cardiopulmonary bypass (CPB), occurring in 8-12% of cases[1, 2, 4]. Commonly labeled “vasoplegic syndrome” (VS), although no universally accepted formal definition exists, it is generally defined as hypotension occurring as a result of low systemic vascular resistance (SVR) in the setting of normal to high cardiac output (CO), and euolemia. Subsequent hypoperfusion can lead to end organ damage and in prolonged catecholamine refractory VS mortality approaches 25% [5, 6].

Routine treatment of vasodilatory hypotension after CPB has mirrored treatment of vasodilatory shock in other inflammatory contexts like sepsis and anaphylaxis. Hemodynamics are supported through both volume optimization as well vasopressors and inotropes. Catecholamines continue to be the most widely used agents with epinephrine, norepinephrine, phenylephrine and dobutamine being available choices. Vasopressin is also commonly used with the pathophysiological basis for its use in these patients being vasopressin deficiency which is believed to contribute to VS. Corticosteroids are another option in patients believed to be steroid deficient and the recent ATHOS-3 trial highlights the possibility of angiotensin II being a therapeutic agent in these patients.[13]

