3.1 General Description

This will be a phase I/II, single-center, double-blind, placebo-controlled, randomized, intent-to-treat study among a placebo group and a group receiving B12a for clinically diagnosed VS after CPB. Subjects will be screened on the medical record and consented in the preoperative area or patient/family will be approached for consent if they are close to qualifying for the study after the surgical procedure. If consent is given they will be enrolled and monitored after cardiopulmonary bypass for cardiac surgery for inclusion criteria as defined in table 1. B12a will be administered as an infusion of 5g for the first dose and must be reconstituted to a 25mg/mL concentration. The initial 5g dose will be given over a period of 15 min. If there is a non-sustained response after the first dose a second dose may be administered within the first 4 hours at the discretion of the primary care team. This strategy is consistent with current FDA approved dosages. If there is no response, rescue with methylene blue will be at the discretion of the primary anesthesiologist or intensivist and will be measured as an outcome. Patients/Legal Authorized Representative (LAR) will be consented on the basis of 1 through 4 and randomized for inclusion based on 5 in the table below. Exclusion criteria are also included table 1. After randomization and drug administration initial vital signs and hemodynamic measurements will be taken. The electronic medical record will then be used to collect patient data retrospectively. Patients will receive 1 follow up phone call at 1 month after enrollment.

[figure not shown]

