3.7 Identification of Source Data

The following source data will be directly recorded on the Case Report Form (CRF):

- Vital signs (T0 \pm 30 min, T0 represents time of drug administration)
 - Cardiac index

- MAP
 - SBP
 - Systolic Pulmonary Blood Pressure
 - Right Atrial Pressure
- Vasopressor infusion rates (T0±30 min, T0 represents time of drug administration)
 - Norepinephrine mcg/kg/min
 - Epinephrine mcg/kg/min
 - Vasopressin unit/min
 - Calcium mg/hour
 - Dopamine mcg/kg/min

The following source data will be directly collected in the Case Report Form (CRF), if we are not able to capture the data in the CRF due to limitations, it will be captured retrospectively in supportive documentation (study source documents, EMR):

- Laboratory tests will be taken as is standard in this patient population with no added tests specific for the study. Results and clinical interpretation will be via the EMR
 - Creatinine, ABG (FiO₂, PaO₂, PaCO₂, pH, Bicarb, Base Deficit, methemoglobin percentage), Lactate, INR, PTT, AST, ALT, Bilirubin, Hemoglobin, platelets
- Vitamin B12 assay and heavy metal quant results 24 hours and 72 hours after drug administration
- Urine output at each 24 hours.
- Vital signs
- Cardiac index at 15 min intervals from administration time T45 through the first 4 hours if the participant has a continuous pulmonary artery catheter. Cardiac index 30 minutes after administration time, times two, followed by every hour for 4 hours if the patient has a non-continuous pulmonary artery catheter and based upon the availability of the technician/therapist.
- MAP at 15 min intervals from administration time T45 through the first 4 hours
- SBP at 15 min intervals from administration time T45 through the first 4 hours
- Systolic Pulmonary Blood Pressure at 15 min intervals from administration time T45 through the first 4 hours
- Right Atrial Pressure at 15 min intervals from administration time T45 through the first 4 hours
- Hospital length of stay (LOS) (Days)
- ICU LOS (Days)
- Ventilator time (Hours)
- End organ dysfunction during the first seven days will not be directly collected in the CRF but will be captured retrospectively in supportive documentation:
 - Stroke (CT or MRI confirmed hemorrhagic or ischemic
 - AKI as defined by AKIN criteria
- New arrhythmias as diagnosed by in the EMR
- Need for mechanical circulatory support (LVAD, ECMO, Intra-aortic Balloon Pump, Impella)

4 Subject Selection Enrollment and Withdrawal

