5.2 Treatment Regimen

- 5g, IV, over 15 min as a single dose. Can order unblinded dose of Cyanokit® within the first 4 hours at the discretion of the primary care team.

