7.2 Statistical Methods

Descriptive Statistics

The primary outcome is change in MAP from baseline over the first 4 hours postoperatively at 15 min increments post randomization. Randomized groups will be compared using analysis of covariance (ANCOVA), adjusting for baseline MAP prior to randomization. A p-value <0.05 is considered statistically significant.

Secondary outcomes will be compared by treatment arms without adjustment for multiple comparisons. Change in rates of vasopressor and inotropic infusions will be compared by

ANCOVA where the outcome is defined as the infusion rate at 30 minute intervals for the first 4 hours post B12a administration and models adjust for the baseline value. Change in systolic blood pressure will be analyzed similarly. Length of stay and ventilator time outcomes will be compared by Wilcoxon rank-sum tests; mortality and binary outcomes will be compared between randomized arms with a Pearson chi-square or Fisher's exact test when appropriate.

As a tertiary aim and exploratory analysis, longitudinally collected data such as daily SOFA score will be modeled in a repeated measures analysis. Treatment groups will be compared by assessing whether B12 treatment affects the slope of or change in SOFA scores over time.

Handling of Missing Data

Missing data is expected to be rare as these outcomes are routinely collected in the electronic medical record. The primary analysis will consider complete cases. Two sensitivity analyses may be performed, including multiple imputation of missing data under the missing at random mechanism and an analysis under the not missing at random mechanism. For the latter, methods may include shared parameter models or worst-case imputation when the cause of the missing data is early mortality

Primary Hypothesis:

The use of an intravenous infusion of vitamin B12a in patients with post-cardiotomy vasoplegic syndrome receiving high dose vasopressors will result in a statistically significant increase in mean arterial blood pressure compared to placebo over the first 4 hours after administration.

Secondary Hypothesis:

The use of an intravenous infusion of vitamin B12a in patients with post-cardiotomy vasoplegic syndrome will have a statistically significant decrease in vasopressor requirement over the first 4 hours after administration.

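### The secondary hypothesis concerns total vasopressor requirement over 4 hours, but Section 7.2 analyses infusion rates at 30-minute intervals and defines no measure of total support

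*Combined protocol and SAP*

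**What the plan says.** The secondary hypothesis in Section 7.2 is that B12a "will have a statistically significant decrease in vasopressor requirement over the first 4 hours after administration". It is the only secondary hypothesis stated, although Sections 2 and 3.5 list many secondary aims.

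The same section describes the analysis, which covers pressors and inotropes alike and refers to their rates in the plural. The method is "ANCOVA where the outcome is defined as the infusion rate at 30 minute intervals for the first 4 hours post B12a administration", with adjustment for the baseline value. Section 7.2 also says that secondary outcomes carry no multiplicity adjustment. It mentions repeated-measures modelling only for tertiary, exploratory data, with daily SOFA score as the example.

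Section 3.7 lists five infusions for the case report form: norepinephrine, epinephrine and dopamine in mcg/kg/min, vasopressin in unit/min, and calcium in mg/hour. The window given is "Vasopressor infusion rates (T0±30 min, T0 represents time of drug administration". For pressure the same section goes further, for example "MAP at 15 min intervals from administration time T45 through the first 4 hours". Section 6 makes the electronic medical record (EMR) the source for data after the first 30 minutes.

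A norepinephrine-equivalent scale is used in the primary objective (Section 2), in eligibility (Section 4.1, Table 1) and in the reasoning about when to treat (Section 7.1). It is tabulated in Appendix Table 1, but it is not applied to the vasopressor outcome.

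**The concern.** Requirement over 4 hours is a statement about total support. A set of rates in different units is not a measure of it, so the phrase infusion rate has no single meaning as an outcome. The analyst would have to decide later which agents to use, whether to sum them, and whether to average the times, model them jointly or test them one by one.

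This matters beyond the secondary hypothesis itself. Sections 1.5 and 8.4 allow vasopressors to be titrated to a pressure ceiling. Part of a B12a effect may therefore appear as less support and not as higher MAP. A reader of the MAP result needs one clear figure for support beside it, and the plan does not define one.

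**Working it through.** The plan gives no numerical target for the vasopressor outcome. The sample size of 50 in Section 7.1 is for MAP only, so there is no figure to reproduce here.

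**1. Is there a combining rule?** The hypothesis refers to requirement, while the objective and the analysis refer to rates. Sections 2, 3.5, 3.7, 6 and 7.2 and the Appendix give no rule for combining agents or times in this outcome.

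**2. What the Appendix scale supplies.** Factors from Appendix Table 1, as equivalents per unit of dose:
- norepinephrine 0.1/0.1 = 1; epinephrine 0.1/0.1 = 1
- dopamine 0.1/15 = 0.0067
- vasopressin 0.05/0.04 = 1.25 per U/min

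Calcium, dobutamine and phenylephrine have no factor.

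**3. What separate rates show and do not show.** Two hypothetical patients (the documents give no frequency of weaning or exchange):

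| | Before | After | Norepinephrine rate | Vasopressin rate | Total equivalents |
|---|---|---|---|---|---|
| A: vasopressin stopped | NE 0.10 + VP 0.04 | NE 0.10 | no change | 0.04 to 0 | 0.10 + 0.04 × 1.25 = 0.15, to 0.10 (−33%) |
| B: agents exchanged | NE 0.15 | NE 0.10 + VP 0.04 | −33% | 0 to 0.04 | 0.15, to 0.10 + 0.05 = 0.15 (0%) |

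In both patients the separate rates, read together, reveal what happened. Neither rate alone gives the change in total, and no planned test does.

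**4. Times.** 240/30 = 8 post-dose times.

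**5. If each time were tested separately for one agent.** Independent tests would give 1 − 0.95^8 = 33.7%. Serial correlation lowers this. A simulation under no effect used the planned baseline-adjusted ANCOVA at each time. It assumed 25 per arm (1:1 allocation), normal data, two-sided 0.05 and 40,000 runs. The documents give neither the allocation ratio nor any correlation. Chance of at least one p<0.05:

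| Assumed correlation | Result |
|---|---|
| Constant 0.5, 0.6, 0.7, 0.8, 0.9 | 29.6%, 28.7%, 28.1%, 26.6%, 25.8% |
| Decaying with time, adjacent 0.7, 0.8, 0.9, 0.95 | 26.4%, 23.4%, 20.8%, 19.3% |
| One ANCOVA on the mean of the 8 times | 4.8% to 5.3% |

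The rate stays high under constant correlation because adjusting for baseline removes much of the shared variation. The residual correlation is ρ/(1+ρ), which is 0.5/1.5 = 0.33 at ρ = 0.5 and 0.9/1.9 = 0.47 at ρ = 0.9. Applying the raw constant correlation to the eight tests without that adjustment gives 24.8% at 0.5 and 11.9% at 0.9, but that is not the planned model.

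**The case against.** The strongest reply is that the analysis matches the listed aim. Sections 2 and 3.5 name change in infusion rates, and Section 7.2 analyses infusion rates; only the word requirement in the hypothesis points to a total. That is fair as to the aim, but the hypothesis is what the trial would report as supported or not, and it is left without a test of its own.

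A reader might infer that the planned analysis would miss a weaned agent or mistake an exchange for a benefit. The documents do not support this. Section 7.2 speaks of rates in the plural, and the examples above mislead only if norepinephrine is read alone.

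A reader might also infer from Section 3.7 that vasopressor rates after 30 minutes go uncollected. They need not: Section 6 sends later data to the EMR, and Section 7.2 defines the outcome to 4 hours. The list is incomplete, which is a drafting matter.

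Section 1.1 mentions "epinephrine, norepinephrine, phenylephrine and dobutamine being available choices", but as general background and not as this trial's regimen. Their absence from Section 3.7 matters only if they are used.

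Finally, Section 7.2 openly leaves secondary outcomes unadjusted, and the same uncertainty about time points affects MAP and systolic pressure. Both statements are true. The missing combination of agents is specific to this outcome.

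**Conclusion.** The point holds as a gap in one secondary outcome. The plan states a hypothesis about total vasopressor requirement and defines no outcome that measures it, although the protocol already contains a suitable scale. Amending it is worthwhile and cheap.

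The 19% to 30% figure is conditional. It needs separate tests at all eight times, which the text neither states nor excludes, together with the assumed correlations, normal data and 25 per arm. It should not be read as the trial's error rate. The 33% changes are illustrations, and the documents do not show how often such changes occur. The preference for a norepinephrine-equivalent total is a judgment about which measure best fits the hypothesis.

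The formal conclusion on MAP does not depend on any of this. What would improve is the reading of MAP under titration and of the secondary hypothesis.

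**What to change.** In Section 7.2, define the vasopressor outcome as the time-weighted mean norepinephrine-equivalent dose from T0 to 4 h, using the Appendix factors for norepinephrine, epinephrine, dopamine and vasopressin. Compare arms by one ANCOVA adjusted for baseline equivalents, and report it beside the MAP result. Show per-agent, per-time rates descriptively.

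Analyse agents without an Appendix factor separately (calcium, and dobutamine or phenylephrine if used), unless a factor is fixed before unblinding.

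State before unblinding how death, mechanical support, methylene blue and open-label Cyanokit within 4 h are handled, and report their frequency by arm. Each can lower the dose without showing an effect of the blinded treatment. Section 3.1 already provides that "rescue with methylene blue will be at the discretion of the primary anesthesiologist or intensivist and will be measured as an outcome", so for methylene blue only the 4-hour window and the handling rule are new. For the open-label drug, Section 5.2 says "Can order unblinded dose of Cyanokit® within the first 4 hours at the discretion of the primary care team", and Section 7.2 has no matching rule.

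In Section 3.7, list the EMR infusion rates from T0+30 min to 4 h explicitly.

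The cost is a few sentences of SAP text and slightly more EMR abstraction for 50 patients. A total hides which agent was weaned, which is why the descriptive rates are kept, and it mixes inotropic with vasopressor use of epinephrine and dopamine.

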4.4 Early Withdrawal of Subjects

- We expect early withdrawals to be rare given it is a single intervention.
- Patients will be free to withdraw consent at any time during the study period.
- Patients who withdraw will be included in intention to treat analysis and safety assessment and analysis.

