5.7.1 Return or Destruction of Study Drug

- As per current Mayo practice.

6 Study Procedures

Patient randomized to B12a or placebo. Data will be measured prospectively for the first 30 minutes and then taken from the EMR after that. All tests besides vitamin B12 assay and heavy metal quant will be done as standard of care and data will only be collected if done as standard of care. Vitamin B12 assay and heavy metal quant will be collected at 24 hours (\pm 1 hour) and 72 hours (\pm 1 hour) after drug administration.

Study Activity	Day 0	Day 1	Day 2	Day 3	Day 4	Day 5	Day 6	Day 7	30 Day F/U
Study Drug	X	X (window -1, -0)							
Informed consent	X	X							
History	X	X							
Concurrent meds	X	X							
Physical exam (Ht, Wt, VS)	X	X							
Patient monitoring for inclusion	X	X							
Randomization Res Pharm	X	X							
CBC w/diff, plts	X	X	X	X	X	X	X	X	
Serum chemistry ^a	X	X	X	X	X	X	X	X	
INR/PTT/Fib/Plt	X	X	X	X	X	X	X	X	
ABG/Lactate ^b	X	X	X	X	X	X	X	X	
Vitamin B12 Assay ^c		X	X	X	X				
Heavy Metal Quant ^c		X	X	X	X				
Hemodynamic monitoring									
Patient Call for follow up on adverse events and mortality									X

a: Albumin, alkaline phosphatase, total bilirubin, BUN, calcium, chloride, glucose, LDH, phosphorus, potassium, total protein, SGOT [AST], SGPT [13], sodium, creatinine
b: PaO₂, PaCO₂, pH, bicarb, SpO₂, lactate, base deficit
c: Vitamin B12 assay, heavy metal quant to be collected at 24 hour (\pm 1 hour) and 72 hour (\pm 1 hour) after study drug administration

7 Statistical Plan

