9.1 Confidentiality

Information about study subjects will be kept confidential and managed according to the requirements of the Health Insurance Portability and Accountability Act of 1996 (HIPAA).

Those regulations require a signed subject authorization informing the subject of the following:

- What protected health information (PHI) will be collected from subjects in this study
- Who will have access to that information and why

- Who will use or disclose that information
- The rights of a research subject to revoke their authorization for use of their PHI.

In the event that a subject revokes authorization to collect or use PHI, the investigator, by regulation, retains the ability to use all information collected prior to the revocation of subject authorization. For subjects that have revoked authorization to collect or use PHI, attempts should be made to obtain permission to collect at least vital status (long term survival status that the subject is alive) at the end of their scheduled study period.

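### The plan promises intention-to-treat but limits the primary MAP analysis to undefined complete cases, so randomized patients with partial 4-hour data can leave the comparison

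*Combined protocol and SAP*

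**What the plan says.** Section 3.1 describes the trial as a "single-center, double-blind, placebo-controlled, randomized, intent-to-treat study". Section 4.4 adds: "Patients who withdraw will be included in intention to treat analysis and safety assessment and analysis".

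Section 7.2 defines the endpoint and the model: "The primary outcome is change in MAP from baseline over the first 4 hours postoperatively at 15 min increments post randomization", and "Randomized groups will be compared using analysis of covariance (ANCOVA), adjusting for baseline MAP prior to randomization". It does not say how the repeated readings of one patient enter the ANCOVA. On missing data it says: "The primary analysis will consider complete cases". It then allows, without committing to them, multiple imputation under missing at random and an analysis under not missing at random. For the latter it mentions shared parameter models or worst-case imputation when early death caused the gap. Section 7.3 defines all-randomized, all-treated and all-completed populations and ties none of them to the primary analysis.

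On data capture, Section 6 states: "Data will be measured prospectively for the first 30 minutes and then taken from the EMR after that". Section 3.7 lists "MAP at 15 min intervals from administration time T45 through the first 4 hours" among the items meant for the CRF, with retrospective capture from source documents and the EMR where the CRF cannot take them. No time limit for abstraction is given. Under Section 9.1, once a patient revokes authorization the investigator "retains the ability to use all information collected prior to the revocation of subject authorization". Sections 4.4 and 7.2 expect withdrawals and missing data to be rare; neither gives a rate.

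**The concern.** For a patient with a full 4-hour MAP record the two rules agree. For a patient with part of the record they diverge: intention-to-treat keeps the patient and complete-case analysis may not. The plan does not say which rule governs the primary comparison.

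Three routes lead to a partial record: death within 4 hours, withdrawal inside the window, and revoked authorization before the later readings have been obtained. The first is plainly informative, because a patient who dies in the window of a blood-pressure trial is unlikely to have had typical pressures. Dropping such patients breaks the randomized comparison at the point where it matters most.

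The undefined term also leaves room for choice after the data are seen. It could mean all 15-minute readings present, a computable summary, or (by confusion with the all-completed population of Section 7.3) completion of every procedure and the 30-day follow-up. These definitions can give different patient sets.

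**Working it through.** **1. The rules side by side.**
- Patient withdraws after 4 hours, readings available: both rules keep the patient. No conflict.
- Patient withdraws inside the window: Section 4.4 keeps the patient; Section 7.2 drops the patient if complete means a full record.
- Patient dies inside the window: Section 3.1's general label would keep the patient; Section 7.2 may drop the patient. Section 4.4 does not speak to deaths.
- Patient revokes authorization before the later readings are obtained: Section 9.1 expressly preserves what was already collected. The plan does not say whether readings already in the EMR may still be abstracted.
- Patient dies after 4 hours: the primary endpoint is unaffected.

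**2. How much of the endpoint lies outside the prospective 30 minutes.** A 15-minute grid from T15 to T240 has 240/15 = 16 post-dose readings. Those from T45 to T240 number (240 − 45)/15 + 1 = 14, and 14/16 = 87.5%.

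**3. The plan's own sample size.** Section 7.1 gives 50 patients, 7.3 mmHg, power 0.8 and p = 0.05. No SD, allocation ratio, sidedness or dropout allowance is stated, so the 50 cannot be reproduced. Assuming 1:1 allocation, a two-sided test and a normal approximation, it can be solved backwards:
- SD = 7.3 / [(1.960 + 0.842) × √(2/25)] = 9.21 mmHg (9.03 with the t distribution).
- Over a range of assumed SDs the total would be 30 (SD 7), 38 (SD 8), 48 (SD 9), 60 (SD 10) or 86 (SD 12).

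**4. Power if complete-case analysis loses patients.** Power = Φ(7.3 / [9.21 × √(1/n₁ + 1/n₂)] − 1.96), with losses spread evenly over the arms:
- 1 lost (24 and 25): 0.79
- 2 lost (24 and 24): 0.78
- 3 lost (23 and 24): 0.77 to 0.78
- 5 lost (22 and 23): 0.76
- 8 lost (21 and 21): 0.73

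That is about one percentage point per patient.

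**5. Shift in an arm mean (illustration).** If k of 25 patients in one arm are excluded and their mean MAP change is g mmHg below that of the rest, the arm mean rises by (k/25) × g:
- k = 1, g = 10: 0.4 mmHg, or 0.4/7.3 = 5% of the target difference
- k = 2, g = 20: 1.6 mmHg, or 22%
- k = 3, g = 30: 3.6 mmHg, or 49%

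The documents give neither k nor g. Losses in the placebo arm raise its mean and shrink the apparent benefit; losses in the B12a arm enlarge it; equal losses with equal g cancel.

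**6. Strictest meaning of complete (illustration).** If all 16 readings are required and each is missing independently with probability q, the expected number of complete patients is 50 × (1 − q)^16: about 46 (q = 0.5%), 43 (1%), 36 (2%) or 22 (5%). The rates and the independence are assumptions; if gaps cluster within patients, fewer patients are lost.

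**The case against.** The case for leaving the text alone has weight. MAP is charted routinely, so the plan's expectation of few gaps is reasonable. Section 5.5 describes patients as intubated and ventilated, which makes withdrawal by the patient within 4 hours unlikely, although a representative could withdraw them. Early death is not overlooked: Section 7.2 names methods for it. With almost no missing data, complete-case ANCOVA and a repeated-measures model should give much the same answer.

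This limits the size of the problem. It does not settle which rule applies when a record is partial, and rarity does not make death-related loss uninformative in a trial of 50.

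Some stronger readings are tempting but unsupported:
- *Withdrawals and early deaths do drop out of the primary analysis.* They drop out only if 4-hour readings are actually missing and complete is read so as to exclude them.
- *Deaths break the promise in Section 4.4.* That promise concerns withdrawals.
- *A patient who revokes authorization loses 14 of 16 readings.* Section 3.7 sends those readings to the CRF first, and no passage says that abstraction waits for days. Section 9.1 does not equate collected with abstracted, and Section 9.2 counts hospital records and data from automated instruments as source data. It concerns revoked authorization, which is not the same act as withdrawing consent. The documents leave the point open.

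**Conclusion.** The point holds as an unresolved inconsistency about who is in the primary comparison. Intention-to-treat is promised, complete cases are specified, complete is undefined, no population is named, and the analyses that would address the gap are optional. A randomized patient with partial 4-hour MAP data can therefore be excluded, in some cases for a reason tied to the outcome.

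The expected size is modest. If missing data are as rare as the plan expects, the loss is about one percentage point of power per patient, assuming 1:1 allocation, a two-sided test and the back-solved SD of about 9.2 mmHg. A shift in the treatment difference is possible, but neither its size nor its direction can be derived from the documents. A reader might infer that the result would be biased in favour of the drug; that does not follow, because the sign depends on which arm loses patients.

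This should be fixed as a cheap improvement. It does not invalidate the design.

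**What to change.** In Section 7.2, replace the complete-case sentence:
- Name the all-randomized population of Section 7.3 as the primary population.
- Analyse all available 15-minute MAP readings over the 4 hours in a baseline-adjusted repeated-measures model, so that a patient with partial readings is kept. State the treatment contrast and the covariance structure in advance. An unstructured matrix for 16 readings has 16 × 17/2 = 136 parameters, too many for 50 patients.
- Report randomized patients with no post-dose MAP by arm, and include them through the multiple-imputation sensitivity analysis.
- Change *may* to *will* for the multiple-imputation analysis and for the worst-case analysis of deaths within 4 hours. The latter is needed because a repeated-measures model implicitly extrapolates beyond death.

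In Section 4.4, state that readings recorded before withdrawal are used where authorization permits. In Sections 3.7 and 6, require the T45 to T240 data to be abstracted promptly after the 4-hour window.

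The cost is a few sentences, slightly more analysis work and less freedom over when abstraction is done. No new patients, tests or data are needed.
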